While our team initially intended to engage clinicians who were part of the ERGO study, due to significant staff turnover at participating hospitals (Brigham and Women's Hospital and Israel Deaconess Medical Center), we instead independently recruited clinicians with no connection to ERGO through existing networks, including direct invitations and advertisements over medical listservs. For ERGO report-back, clinicians (n=3) had no previous affiliation with the ERGO study and included one physician assistant, one genetic counselor, and one pediatric physician. Training sessions for clinicians returning results to ERGO participants took place over two virtual sessions totaling two hours and 30 minutes, and included the same components as the PROTECT training. In addition, as clinicians sharing results with ERGO participants had no previous experience with the study and requested additional support, they received a script to use during the report-back session.

Clinicians met with participants assigned to the clinician-guided report-back group in brief (20-30 minutes), one-on-one appointments. In PROTECT, participants travelled to study-

affiliated community health clinics to review their online reports with a clinician, whereas ERGO appointments took place virtually through Zoom and clinicians shared their screen. At the end of the appointment, participants were given the access code to log into their reports so they could revisit them independently. Participants assigned to the self-guided group logged into their online reports independently and did not review their results alongside a clinician or other research staff.

Pre- and post-surveys

Participants completed a 15-minute pre-survey at baseline and a 20-minute post-survey at least two weeks after accessing their reports. Surveys were comprised of a series of questions across domains, including feelings, satisfaction, perceived self-efficacy, knowledge, exposure behaviors, and, for PROTECT only, study relationships.

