For the feelings section, using a six-point Likert-scale (from “Not at all” to “Very Strong”), participants rated how strongly they experienced feeling respected, empowered, worried, and (post-survey only) surprised in relation to report-back. Satisfaction was assessed in the post-survey across four questions using a 5-point Likert scale from “Strongly disagree” to “Strongly agree.” In the knowledge section, participants were asked to answer whether a series of statements were “True”, “Probably true”, “Probably false”, or “False.” The knowledge section contained 9 questions in ERGO and for PROTECT, two additional knowledge questions relevant to compounds included in PROTECT reports. The perceived self-efficacy section asked participants to rate their confidence across seven different statements using a seven-point scale from “Cannot do it at all” to “Highly certain I can do it.” In the exposure behaviors section, participants rated how frequently they performed certain actions using a four-point scale from “never” to “almost every day” or from “never” to always.” The post-survey behavior section also included yes/no questions about changes made after receiving reports and open-ended questions for further elaboration. In PROTECT, pre- and post-surveys also included a set of questions asking about relationships to clinical care and the PROTECT study, which participants answered on a five-point scale from “strongly disagree” to “strongly agree.” For each question, participants also had the option to select “Don’t Know” or “Decline to Answer.” Full survey instruments can be found in supplemental material.

Based on the preferences of partnering study teams for participant communications, PROTECT participants completed pre- and post-surveys over the phone with a study staff member or PROTECT-affiliated nurse who was not involved directly in reporting back results to participants, while ERGO participants completed surveys online in REDCap, a web application for building and managing surveys.

Survey Analysis

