All data analysis was restricted to participants who completed the pre- and post-surveys and viewed their DERBI reports. We first conducted stratified analyses to summarize participant responses across domains and characterize changes before and after report-back. For each cohort and intervention group, we calculated descriptive statistics on pre- and post-survey responses. To assess pre- and post-survey changes over time, we used Wilcoxon signed-rank tests with the Pratt method. For the knowledge section, true/probably true and false/probably false questions were re-coded to indicate correctness, and McNemar's tests were conducted to assess changes in item-level responses.

To further explore the impact of the interventions, we used multiple regression to model survey responses of both cohorts and intervention groups (clinician-guided and self-guided). Our main model was a linear mixed effects model that included intervention group, cohort, and survey timepoint as predictors and an interaction between survey time point and intervention group. We also included a random intercept for each participant. Report-back group and cohort were factorized with the online-only group and the PROTECT cohort as reference levels.

Self-efficacy was modeled as a scale by summing responses across all self-efficacy questions for each participant at the pre- and post-survey. Internal consistency of the self-efficacy scale was evaluated using Cronbach's alpha. Knowledge was modeled as an index, and we summed the number of correct responses and normalized to the number of questions included in the survey (11 questions in PROTECT and 9 in ERGO). For binary yes/no behavior changes, we used an analogous logit link function. For post-survey-only outcomes (the feeling "surprised", satisfaction, and behavior changes), we used multiple regression models that included fixed effects for intervention group and cohort only (no random effect).

To evaluate the robustness of these models, sensitivity analyses were conducted by comparing our main regression models with alternate models. Model performance was compared using Akaike Information Criterion (AIC) and we report model effect estimates and confidence intervals for key predictors. All analyses were conducted using R version 4.1.1 using the `lm()` and `lmer()` functions from the `stats` and `lme4` packages, respectively.

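### The models for the yes/no behaviour-change items omit the behaviour frequency recorded in the pre-survey, which gives up precision and protection against chance imbalance and leaves the effect among those able to change unestimated

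*Combined protocol and SAP*

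**What the plan says.** The Pre- and post-surveys section describes two kinds of behaviour question.

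- Frequency items: "participants rated how frequently they performed certain actions using a four-point scale". Exposure behaviours are listed as a domain of both surveys ("Surveys were comprised of a series of questions across domains, including feelings, satisfaction, perceived self-efficacy, knowledge, exposure behaviors"). The section marks the feeling of surprise, satisfaction and the yes/no items as post-survey, but puts no such limit on the frequency items. The baseline survey ("Participants completed a 15-minute pre-survey at baseline") therefore contains them.
- Change items: "The post-survey behavior section also included yes/no questions about changes made after receiving reports and open-ended questions for further elaboration". These exist only after report-back.

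The Survey Analysis section uses a logit link for the change items ("For binary yes/no behavior changes, we used an analogous logit link function") and groups them with the other post-survey-only outcomes, for which "we used multiple regression models that included fixed effects for intervention group and cohort only (no random effect". No baseline behaviour term appears. The section does not say how someone already performing an action is coded, and it describes no analysis restricted to people not yet performing it. The sensitivity analyses compare the main models with alternate models whose content is not given. Item wording is in a supplement outside the document.

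**The concern.** A question about whether a change was made depends on where the person started. Someone who already performs a protective action at the highest frequency has little room to report a change, so baseline frequency may predict the answer strongly. A model with only group and cohort leaves that explainable variation in the error.

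Three things are at stake:

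- **Precision.** The arm contrast is less precise than the collected data allow.
- **Chance imbalance.** If more people in one arm already perform the action, the arm estimate moves, and nothing in the model corrects it.
- **Interpretation.** If people with no room to change give the same answers in both arms, the contrast over everyone is smaller than the effect among those who could change. The plan offers no estimate of the latter.

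Behaviour change is the outcome of report-back closest to action, so a clear reading of it matters.

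**Working it through.** The plan states no sample size, power, alpha, effect size or behaviour rates, so there is no figure of its own to reproduce. Every rate below is an assumption.

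**1. Dilution of the average effect.** Let q be the share already performing the action, r their rate of yes (equal in both arms), and p0 and p1 the rates of yes among the rest. Each arm's rate is (1 − q)p + qr, so the risk difference is (1 − q)(p1 − p0), whatever the value of r.

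- With p0 = 0.30 and p1 = 0.50, q = 0, 0.2, 0.4 and 0.6 gives risk differences of 0.20, 0.16, 0.12 and 0.08. If r = 0, the odds ratios are 2.33, 2.11, 1.95 and 1.83.
- With q = 0.30, r = 0.05, p0 = 0.50 and p1 = 0.75 (odds ratio 3 among the rest):
  - self-guided: 0.7 × 0.50 + 0.3 × 0.05 = 0.365
  - clinician-guided: 0.7 × 0.75 + 0.3 × 0.05 = 0.540
  - odds ratio: (0.540/0.460)/(0.365/0.635) = 2.04; risk difference 0.175

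**2. What adjustment does to that average.** In 400,000 simulated records from the second scenario, the raw and standardised risk differences were both 0.177. Adjustment targets the same average effect. Only an analysis of those able to change targets the odds ratio of 3.

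**3. Precision with a perfect indicator.** Simulated logistic models, likelihood-ratio tests at two-sided 5%, 2,000 replicates per setting, p0 = 0.50 and p1 = 0.75. Power (%) without → with an indicator of already performing the action:

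| q | r = 5%, 50/arm | r = 5%, 80/arm | r = 20%, 50/arm | r = 20%, 80/arm |
|---|---|---|---|---|
| 10% | 62.5 → 68.5 | 81.1 → 86.9 | 64.4 → 68.3 | 84.4 → 87.2 |
| 20% | 51.7 → 62.5 | 72.4 → 83.2 | 52.8 → 58.7 | 73.1 → 78.4 |
| 30% | 42.2 → 55.5 | 61.3 → 76.2 | 43.0 → 47.5 | 59.8 → 66.9 |
| 40% | 35.3 → 48.4 | 50.2 → 67.5 | 34.5 → 41.6 | 47.1 → 56.5 |

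Gains run from 2.8 to 17.3 points. Rejection under no effect was 4.6% to 6.4%. An independent repeat at q = 30%, r = 5% gave 44 → 56 at 50 per arm and 59 → 76 at 80.

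**4. Precision with weaker information.** In the q = 30% settings, a continuous score correlated 0.3 with the indicator gained about 0 to 1 point, and one correlated 0.5 about 0 to 4 points. With a perfect indicator but r of 40% to 50%, the gain was about 1 to 4 points; power did not fall.

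**5. Chance imbalance.** Suppose there is no effect, with 50% yes among those not yet acting and 5% among those already acting. Let 40% of the self-guided and 25% of the clinician-guided arm already act.

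- self-guided: 0.60 × 0.50 + 0.40 × 0.05 = 0.320
- clinician-guided: 0.75 × 0.50 + 0.25 × 0.05 = 0.3875
- apparent odds ratio: (0.3875/0.6125)/(0.320/0.680) = 1.34

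The SD of a chance difference at 30% is √(2 × 0.3 × 0.7/n): 0.092 at 50 per arm and 0.072 at 80. A gap of 0.15 is therefore about 1.6 to 2.1 SD: possible, but not typical.

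**The case against.** The strongest reply is that the plan's estimate is not wrong. Under random assignment the unadjusted contrast is a valid average effect over those analysed, and ordinary confidence intervals already allow for chance imbalance. That stands, with the reservation that one ERGO participant was not randomised and that the analysis is limited to completers who viewed their reports.

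A reader might infer three stronger things that the documents do not support.

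- *That people already acting are counted as no change.* Item wording, skip rules and any option for those already acting are in the unseen supplement. Such a person could report a further change, the items may not match the frequency items, and some frequency items may describe habits that raise exposure.
- *That the planned odds ratio is biased and a covariate would restore the larger one.* The 2.04 and the 3 answer different questions, and step 2 shows that a standardised risk difference does not move the average.
- *That a real benefit would probably be missed.* The largest power gains need a perfect indicator and favourable assumed rates.

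It can also be said that baseline behaviour is used elsewhere, because the frequency items can be compared before and after and fall under the mixed model. That is fair, but it does not improve the yes/no models. Nor do the alternate models, since none is said to contain a baseline behaviour term. Finally, the section is in the past tense, so an item mapping chosen now could be post hoc. That affects how the analysis should be labelled.

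**Conclusion.** The concern holds as a matter of precision and interpretation. A baseline measure of the same domain was collected and is left out of the yes/no behaviour-change models. The arm contrast remains valid as an average, but it forgoes precision and protection against chance imbalance to the extent that baseline behaviour predicts the answer. The effect among those with room to change is not estimated.

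The size cannot be derived from the documents. On the assumptions shown, the power gain lies between about 0 to 4 points for an imperfectly related score and about 17 points for a perfect indicator. The understatement of the effect among those able to change is conditional: it requires that people already acting mostly answer no or, more generally, that their answers do not differ by arm. This is an inexpensive improvement worth making; it does not invalidate the planned analysis.

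**What to change.** - State how a participant already performing an action is coded on each yes/no item.
- In each yes/no model, add the matching pre-survey frequency item alongside group and cohort. Where none matches, add a mean pre-survey behaviour score, coded so that higher is more protective.
- Report the arm effect as a standardised risk difference with its confidence interval.
- As a supporting analysis, estimate the arm effect among participants not already at the most protective pre-survey response. Adjustment alone does not supply this.
- Fix the item mapping and coding without regard to results. If results are final, present all of this as a labelled sensitivity analysis.

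No new data are needed. The costs are one extra parameter per model, the mapping work, a smaller sample in the supporting analysis, and a few participants with a non-substantive baseline answer, who would drop out unless a missing indicator is used. According to the Study design overview, assignment came before recruitment and the baseline survey, so the text should also say that the pre-survey answers are taken to be unaffected by assignment.
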